10.5. Secondary Endpoints

10.5.1. 6 Minute Walk Test

The 6 minute walk distance (6MWD) results, as well as their changes from baseline will be described by patient and visit and summarized by visit. The within patient changes from baseline will be tested for each applicable visit using the paired t test.

Supportive analyses will include:

- An ordinary ANCOVA (again after multiple imputation for missing values) will be applied. The model will include the stratification factors as strata and baseline as a covariate.
- An analysis of time to persistent 10% worsening using Kaplan-Meier method and Cox regression
- A repeat of the primary ANCOVA analysis on the 6MWD after it has been converted to percent-predicted 6MWD by means of a relevant reference equation [Geiger 2007]
- A comparison of the percentage of responders (<10% worsening of 6MWD at Week 48) and progressors (\geq 10% worsening of 6MWD at Week 48)
- An exploration of the treatment effect in 6MWD in the context of the following:
 - o the protocol-specified stratification factors
 - o baseline height, baseline weight, and baseline BMI
 - o Stop codon type
 - o Exon location

In all relevant analyses, compliant patients who become nonambulatory (unable to perform the 10 meter run/walk test in \leq 30 seconds) during the study will be assigned a 6MWD of zero from the timepoint at which the patient becomes nonambulatory.

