10.5.2. Timed Function Tests (TFTs)

The results of the timed function tests (the time taken to stand from a supine position, time taken to run/walk 10 meters, and time taken to climb/descend 4 standard-sized stairs) in those patients who have the ability, as well as the changes from baseline will be described by patient and visit and summarized by visit and overall. The within patient changes from baseline will be tested for each applicable visit using the paired t-test. Patients who cannot perform a test within 30 seconds will be assigned 30 seconds as their result.

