### 5.8.4. Timed Function Tests

Timed function test data (ie, time to stand from supine, time to run/walk 10 meters, time to climb 4 stairs, and time to descend 4 stairs) and change from baseline to each post baseline visit will be summarized descriptively by visit for ambulatory subjects with non-missing baseline timed function tests assessments. Similarly the time to stand from supine, time to run/walk 10 meters, time to climb 4 stairs, and time to descend 4 stairs will also be summarized for each actual age.

Timed function test (TFT) data imputation rules as the following will be used in the summary.

- If time to run/walk 10 meters > 30 sec, then set to 30 sec.
- If time to stand from supine > 30 sec, then set to 30 sec.

The Kaplan-Meier method will be applied to the analysis of age at loss of ambulation. The median age at loss of ambulation will be reported by treatment group in studies 020/020e (ataluren/ataluren, placebo/ ataluren, and overall), corticosteroid use duration (<12 months,  $\geq$ 12 months), and corticosteroid type (deflazacort vs prednisone/prednisolone) at baseline. The Kaplan-Meier curves will also be displayed. The age at loss of ambulation is defined as age of the disease progression reported as the adverse event. The subjects who are ambulatory at the end of study or discontinuation will be censored on the last valid visit date. Age on that date will be used in the analysis.

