### 8.3. Analyses Based on Matched Populations of CINRG and Study 020e

Demographics and baseline characteristics (age, race, ambulation status, corticosteroid use (yes or no), duration of corticosteroid use, corticosteroid type, baseline 6MWD, baseline time to run/walk 10 meters, baseline time to stand from supine, baseline %-predicted FEV1, %-predicted FVC, PEF, NSAA total score) will be summarized descriptively for CINRG and Study 020e

based on each matched population. The summary will be displayed by corticosteroid use (yes vs no) and cumulative steroid use ( $\geq 12$  months vs  $< 12$  months) for baseline ambulatory and non-ambulatory subjects separately. The baseline is defined as the first visit in CINRG data. The comparison to the natural history data (ie, CINRG data) based on matched subjects will be performed in FVC using piece-wise regression models and age to loss of ambulation using Kaplan-Meier method.

Piece-wise regression models will be applied to log FVC in CINRG and study 020e data, separately, using different ages as the changepoint. The most possible changepoint in terms of age will be chosen at the best model fit (ie, AICC value is the maximal). Scatter plots of log FVC and the most fitted piece-wise regression line will be generated for CINRG and study 020e, separately. Comparison between the observed and predicted FVC in study 020e will be performed using repeated measures analysis of variance to account for within-subject correlation, where the predicted values are based on the regression equation estimated by the best fit regression model based on CINRG data.

In study 020e, the loss of ambulation is defined as the disease progression reported as the adverse event or the time to run/walk 10 meters  $> 30$  seconds, whichever occurs earlier. The event age is the one on the AE start date. The subjects who are ambulatory at the end of study will be censored on the last valid timed function tests assessment date. Age on that date will be used in the analysis. In the CINRG data, the age at the earliest report of the non-ambulation or the time to run/walk 10 meters  $> 30$  seconds, whichever earlier, will be picked as the event age. If subjects in CINRG data do not report non-ambulation, the age at the last report of ambulation will be chosen as the censor age. A sensitivity analysis will be performing based on the loss of ambulation defined only by disease progression AE.

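### SAP 8.3: the 10 m timed trigger for loss of ambulation misses 020e boys who cannot do the test, so without a progression AE their loss has no event rule, while CINRG counts a direct report

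*SAP*

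**What the plan says.** SAP 8.3 compares age at loss of ambulation between Study 020e and the CINRG registry by Kaplan-Meier.

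- **020e event.** The "loss of ambulation is defined as the disease progression reported as the adverse event or the time to run/walk 10 meters" above 30 seconds, whichever is earlier.
- **020e event age.** "The event age is the one on the AE start date". No date is given for an event found by the timed test.
- **020e censoring.** "The subjects who are ambulatory at the end of study will be censored on the last valid timed function tests assessment date".
- **CINRG event.** "In the CINRG data, the age at the earliest report of the non-ambulation or the time to run/walk 10 meters" above 30 seconds, whichever is earlier. No AE is needed.
- **Sensitivity analysis.** Loss of ambulation defined by the progression AE alone.

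Three other rules bear on the timed test:

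- Protocol 10.5.2: "Patients who cannot perform a test within 30 seconds will be assigned 30 seconds as their result".
- SAP 5.8.4: "If time to run/walk 10 meters > 30 sec, then set to 30 sec". This is introduced as a rule for the summary in that section. SAP 8.3 neither adopts nor excludes it.
- Protocol 10.5.1 calls a patient nonambulatory when he is "unable to perform the 10 meter run/walk test in" 30 seconds or less. That covers a boy who cannot do the test at all.

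For the NSAA, SAP 5.8.5 has an explicit rule for inability (the item scores zero). The SAP has no such rule for the timed tests.

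**The concern.** A boy who loses ambulation will often go from a measurable time to no time. A trigger that needs a recorded time strictly above 30 seconds does not see that transition, and a 30-second cap or assignment hides slow completers as well. What remains in 020e is the AE. CINRG keeps a second working route, the direct report. If some 020e losses carry neither an AE nor a recorded time above 30 seconds, true events drop out of one group only and the 020e curve moves to later ages without any drug effect. SAP 8.1 gives the purpose of the CINRG comparison as assessing long-term treatment benefit, so the direction of such an error matters.

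The planned sensitivity analysis cannot show the problem. It removes the timed trigger and so counts no more 020e losses than the main rule.

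**Working it through.** The plan gives no event count, power or AE capture rate for this comparison, so there is no figure to reproduce. The check has two parts.

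**1. Does the timed trigger fire?** The condition of a time strictly above 30 s, applied to three boys under each reading of the data:

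| Boy | Raw time | After the SAP 5.8.4 cap | After the Protocol 10.5.2 assignment |
|---|---|---|---|
| Completes in 28 s | no | no | no |
| Completes in 35 s | **yes** | no (30 is not above 30) | no |
| Unable, no time | no (missing) | no (missing) | no (30 is not above 30) |

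The boy who is unable is missed under every reading. The slow completer is caught only on raw times. Under the Protocol 10.5.1 definition both are nonambulatory.

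**2. What would missed losses do?** Let *a* be the share of 020e losses with a progression AE and *r* the share with a recorded raw time above 30 s, taken as independent. The share missed by both triggers is

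m = (1 − a)(1 − r).

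If the missed losses are a random subset and are censored shortly before the event, the apparent 020e hazard is about (1 − m) times the true one. With no true difference the hazard ratio (020e to CINRG) is then about 1 − m.

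This was checked by simulation. All inputs are assumptions except the 144 weeks, the 12-weekly tests and the 7-14 entry age (SAP 8.2):

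- True age at loss is normal, with median/SD of 12/2, 13/2 or 14/3 years, and is the same in both groups.
- Entry age is uniform over 7-14, with boys ambulatory at entry.
- Follow-up is 144 weeks in both groups.
- CINRG captures every loss.
- Missed 020e losses are censored at the last 12-weekly test.
- There are 3000 boys per group and one run per scenario.
- Late entry is not adjusted for in either group.

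Ranges are over the three age distributions:

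| a | r | m | 1 − m | Simulated HR | 020e median minus CINRG (years) |
|---|---|---|---|---|---|
| 1.00 | 0 or 0.5 | 0 | 1.00 | 1.00 to 1.11 | −0.32 to +0.06 |
| 0.95 | 0 | 0.05 | 0.95 | 0.93 to 0.96 | 0.07 to 0.13 |
| 0.90 | 0 | 0.10 | 0.90 | 0.89 to 1.00 | 0.05 to 0.20 |
| 0.80 | 0 | 0.20 | 0.80 | 0.77 to 0.87 | 0.27 to 0.36 |
| 0.60 | 0.5 | 0.4 × 0.5 = 0.20 | 0.80 | 0.81 to 0.83 | 0.34 to 0.51 |
| 0.60 | 0 | 0.40 | 0.60 | 0.60 to 0.61 | 0.83 to 1.12 |

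The first row shows the simulation noise. The 5% and 10% rows lie close to it, so there the formula is the better guide. The two rows with m = 0.20 show that what matters is the share missed by both triggers, not the share without an AE.

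A second simulation used 200 boys per group, true age at loss normal with mean 13.5 and SD 2.2, a Cox model with delayed entry, and follow-up of up to 3.7 years in 020e. At 20% missed it gave HR 0.82 and medians of 13.9 and 13.5, a difference of 0.4 years. Its follow-up exceeds the planned 144 weeks (144/52 ≈ 2.8 years), so it serves only to confirm the order of size.

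**The case against.** Four points on the other side carry weight.

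- **The cap may not apply.** SAP 5.8.4 ties it to its own summary, and a criterion of more than 30 seconds makes sense only on uncapped times. The 30-second assignment is in the protocol, and SAP 1 says the SAP prevails where the two conflict. A reader might infer that the timed trigger can never fire. The documents do not support that: on raw times it fires for a boy who completes the distance slowly. What stands is that the SAP leaves the choice open, and that a boy with no time is missed either way.
- **Censoring of lost walkers is not written.** A reader might infer that SAP 8.3 censors them. The rule covers boys still ambulatory at the end of study, so a boy who has stopped walking without meeting a trigger fits neither rule. Censoring at his last valid timed test is the likely programming result, but it is not an instruction.
- **AEs may capture most losses.** Protocol 8.1.1 makes worsening of an existing illness reportable, 8.1.2 says progression of the dystrophinopathy is to be reported as an AE, and 7.13 has AEs assessed at every visit. With near-complete capture the bias is negligible. Against this, no passage requires a specific, dated loss-of-ambulation AE, and Protocol 10.4.3 rules out reconciling caregiver-reported outcomes with AE reports.
- **The AE half could also err the other way.** Disease progression is wider than loss of ambulation. If other progression AEs were counted, 020e would gain early events, to ataluren's disadvantage.

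A reader might also look for a false-positive rate. SAP 8.3 specifies Kaplan-Meier for this endpoint with no test or significance level, so no such rate can be attached to the plan.

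**Conclusion.** The point holds as a gap in specification with unequal ascertainment. Followed literally, the 020e rule misses boys who cannot do the test and have no progression AE, while the CINRG rule would count the same boys once non-ambulation is reported. A loss found only by the timed test also has no defined event age.

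Losses missed by both triggers bias the comparison toward ataluren. With no true difference, 20% missed corresponds to a hazard ratio near 0.8 and a median about 0.3 to 0.4 years later; 5% missed corresponds to about 0.93 to 0.96. These sizes assume that missed losses are a random subset, are censored at the last timed test, and that CINRG captures all of its own. The documents do not give the true share, and it could be close to zero.

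The comparison lies outside the CSR (SAP 1) and the primary objective is safety, so the consequence is confined to the long-term benefit claim. The rule should be corrected before that claim is made.

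**What to change.** In SAP 8.3:

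1. State that the timed trigger uses raw times, before any 30-second cap or assignment.
2. Define it by the Protocol 10.5.1 criterion, inability to complete the 10 m run/walk in 30 seconds or less. Count a recorded time above 30 s, a test stopped at 30 s, and a test not done because ambulation was lost.
3. Date it at the first such visit, and take event age from the earlier of that date and the AE start date.
4. State that boys meeting the criterion are events and are not censored at an earlier timed test.
5. Apply the same criterion to CINRG where the transferred data allow, and say where they do not.

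The cost is a few sentences, a small derivation change, and use of the recorded reason a test was not done. The documents do not show whether that reason is coded in either source, so this needs checking first. The 020e median may come out earlier and less favourable. If AE capture proves complete, the result does not change.

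### SAP 8.3 defines loss of ambulation in 020e as the earlier of two triggers but gives only the AE start date as event age, so test-first events are dated late and test-only events have no date

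*SAP*

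**What the plan says.** SAP 8.3 sets out the Kaplan-Meier comparison of age at loss of ambulation between 020e and CINRG.

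- **020e, definition.** "the loss of ambulation is defined as the disease progression reported as the adverse event or the time to run/walk 10 meters" exceeding 30 seconds, "whichever occurs earlier".
- **020e, date.** The next sentence reads: "The event age is the one on the AE start date". No other event date is given.
- **020e, censoring.** Boys still ambulatory when the study ends "will be censored on the last valid timed function tests assessment date".
- **CINRG, definition and date.** "In the CINRG data, the age at the earliest report of the non-ambulation or the time to run/walk 10 meters" exceeding 30 seconds, "whichever earlier, will be picked as the event age".
- **CINRG, censoring.** Where non-ambulation is never reported, "the age at the last report of ambulation will be chosen as the censor age".
- **Sensitivity analysis.** Loss of ambulation defined by the disease-progression AE alone.

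SAP 5.8.4 has a separate, within-study analysis of age at loss of ambulation. It defines the event by the AE only and takes the age at that AE, so its definition and date agree. The same section caps 10 m times above 30 seconds at 30 seconds for the summaries.

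**The concern.** Both cohorts have a two-trigger definition that takes the earlier trigger. In CINRG the date follows the trigger. In 020e the date is tied to one trigger whichever came first. A boy who first exceeds 30 seconds on the 10 m test and has a progression AE recorded later is an event at the test by definition, but is dated at the AE. A boy who exceeds 30 seconds and never has a progression AE meets the definition with no event date. The censoring sentence does not cover him either, because it applies to boys who are still ambulatory.

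This comparison is one of two that SAP 8.3 plans against natural history (the other is FVC), and SAP 8.1 says the purpose is to assess long-term treatment benefit. A rule that dates some events later in the treated cohort only can look like such a benefit.

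**Working it through.** The plan states no event count, median or power for this comparison, so there is no figure to reproduce. The check sets the rules side by side and then sizes the delay for a single event.

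**1. Rules by case**

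| Case | Event under the definition | 020e date as written | CINRG date |
|---|---|---|---|
| AE (020e) or report (CINRG) comes first | AE or report | AE start: agrees with the definition | report |
| Test over 30 s first, AE or report later | test | AE start: late by the gap | test |
| Test over 30 s, no AE or report | test | none given | test |

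The rule fails in rows 2 and 3 and works in row 1.

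**2. Effect on the sensitivity analysis.** Taken literally, every 020e event that has a date is dated by its AE. The main analysis then has the same dated events as the AE-only sensitivity analysis. The two differ only in how the row 3 boys are handled, so the sensitivity analysis tests very little.

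**3. Delay for one test-first event.** Clinic visits in 020e are every 12 weeks (SAP 2), and the 10 m test is done at each of them (SAP Table 1). Delay in years = weeks × 7 / 365.25.

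- One visit: 12 × 7 / 365.25 = 0.23
- Two visits: 24 × 7 / 365.25 = 0.46
- Four visits: 48 × 7 / 365.25 = 0.92

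**4. Direction.** A later event age keeps the boy in the risk set as ambulatory for longer. A row 3 boy who is censored removes an event. Both raise the 020e curve and leave CINRG unchanged.

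**5. Illustration of the effect on the median.** Every input here is an assumption, not a document value. True age at loss is normal with mean 13 and SD 2.5 years, entry age is uniform from 7 to 14, follow-up is 144 weeks, and the Kaplan-Meier estimate allows for delayed entry. The disease is identical in both cohorts, so any difference is artefact. The reference median is 13.02 years. Shift of the 020e median, in years:

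| Share of events affected | AE 12 weeks after test | AE 48 weeks after test | No AE, censored at age of loss |
|---|---|---|---|
| 10% | 0.04 | 0.14 | 0.23 |
| 25% | 0.10 | 0.36 | 0.63 |
| 50% | 0.21 | 0.79 | 1.68 |

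The documents give neither the share of affected events nor the gap. The table shows direction and sensitivity to those two unknowns. It does not estimate the bias in this study.

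**The case against.** The strongest reply is that the sentence about the AE start date was meant only for AE-triggered events. A test carries its own date, whereas an AE has an onset and a resolution date (protocol 8.3), so the author had to say which applied. An AE-only sensitivity analysis also makes most sense if the main analysis uses test dates. This is a plausible account of the intent. The text does not say it, however, and even on this reading test-triggered 020e events have no dating rule. The sentence needs correcting either way.

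A second reply is that test-only events should be uncommon. Protocol 8.1.1 makes worsening of a pre-existing illness reportable, and protocol 8.1.2 expects disease progression to be recorded as an AE. That stands as a reason why row 3 may be small. But nothing in the plan links a test over 30 seconds to the filing of an AE or fixes its start date, so row 2 remains open.

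A reader might also infer more than the documents support:

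- **That no 020e event age is comparable with CINRG.** Where the AE is the earlier trigger, its start date is the trigger date and the rule works.
- **That CINRG ages are systematically late because they are visit dates.** The documents give no CINRG visit interval and do not say how a report is dated. The 020e test dates also sit on a 12-week grid, so they carry a lag of the same kind.
- **That the result is uninterpretable, or that it is the study's main finding.** No document figure shows the first. On the second, SAP 1 places the Section 8 analysis outside the CSR, and the primary objective is safety.
- **That interval censoring is required.** Taking the earlier of the two dates closes the gap. Interval censoring between assessments would discard the AE onset date and is a matter of preference.

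**Conclusion.** Wrong as written, and it should be corrected. The 020e dating rule in SAP 8.3 does not follow its own definition when the 10 m test is the first trigger, and it gives no date when the test is the only trigger. The CINRG rule has neither problem. Each test-first event is late by the gap between test and AE, 0.23 years per 12-week visit. Undated events are lost if they are censored. Both effects favour ataluren.

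The total shift cannot be estimated from the documents, because they give neither the share of test-first or test-only events nor the lag to the AE. The conclusion on direction assumes that the sentence is programmed literally and that undated events are censored. The effect is confined to the CINRG comparison of age at loss of ambulation. The AE-only analysis in SAP 5.8.4 and the primary safety analysis are untouched.

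**What to change.** Replace the dating sentence in SAP 8.3 with a rule that sets the 020e event age at the earlier of (a) the start date of the disease-progression AE and (b) the date of the first 10 m run/walk over 30 seconds. State that (b) applies when no AE was filed. State also that the trigger uses recorded times before the 30-second cap in SAP 5.8.4, since a capped value can never exceed 30. Keep the AE-only definition as the sensitivity analysis, which then differs from the main analysis in substance.

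The cost is one or two sentences in the SAP and a small change to the derivation of the event date. It needs no new data, because the 10 m times and their dates are already collected at every visit.

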## 10. DOCUMENT HISTORY

Version Number	Author	Description
Version 1	██████	Initial version – Sept. 18, 2018
Version 2	██████	Jan. 23, 2019 Removed the comments that accidentally left in the document Corrected document date in the header.
